[figure not shown]
[figure not shown]

Study information

Title	A Retrospective Registry Based Study for Evaluating Treatment Response in Patients Targeted Treated with Metastatic Renal Cell Carcinoma (mRCC) with Sunitinib in First-line Therapy
Protocol number	A6181235
Protocol version identifier	3.0
Date	18 November 2022
Active substance	Sunitinib
Research question and objectives	
Primary Objective:
 
• Evaluation of Sunitinib treatment responses/objective response rate according to disease risk group in patients with mRCC targeted treated with Sunitinib in first-line therapy in Turkey 
Secondary Objectives:
 
• Evaluation of survival and treatment response to Sunitinib treatment regimen,• Determination of factors affecting the treatment regimen change and the frequency of these factors in patients with mRCC• Determination of demographic, clinical and pathological characteristics of patients with mRCC• Determination of median duration use of patients using interferon (IFN)

PFIZER CONFIDENTIAL

Author	Assoc. [name] [REDACTED]
Co-author	PPD [REDACTED]

This document contains confidential information belonging to Pfizer. Except as otherwise agreed to in writing, by accepting or reviewing this document, you agree to hold this information in confidence and not copy or disclose it to others (except where required by applicable law) or use it for unauthorized purposes. In the event of any actual or suspected breach of this obligation, Pfizer must be promptly notified.

PFIZER CONFIDENTIAL

[figure not shown]
[REDACTED]

2. LIST OF ABBREVIATIONS

[figure not shown]
Abbreviation	Definition
ACE-I	Angiotensin Converting Enzyme Inhibitor
AE	adverse event
AEM	Adverse Event Monitoring
ARB	Angiotensin Receptor Blockers
ARDS	acute respiratory distress syndrome
CRF	Case Report Form
CRO	Contracted Research Organization
DCT	Data Collection Tool
ECOG	Eastern Cooperative Oncology Group
FDA	Food and Drug Administration
GPP	good pharmacoepidemiology practices
HD IL-2	high-dose interleukin 2
IEC	Independent Ethics Committee
IFN	interferon
IMDC	International Metastatic RCC Database Consortium
IQR	interquartile range
IRB	Institutional review board
LN	Lymph node
mRCC	Metastatic Renal Cell Carcinoma
MSKCC	Memorial Sloan Kettering Cancer Center
NIS	non-interventional study

PFIZER CONFIDENTIAL

RCC	Renal Cell Carcinoma
PFS	progression-free survival
SPSS	Statistical Package for Social Sciences
TKI	tyrosine kinase inhibitor
VEGF	vascular endothelial growth factor

PFIZER CONFIDENTIAL

4. ABSTRACT

A Retrospective Registry Based Study for Evaluating Treatment Response in Patients Targeted Treated with Metastatic Renal Cell Carcinoma (mRCC) with Sunitinib in First-line Therapy, dated 18 November 2022 and with version number of 3.0.

Objectives:

The aim of this study is to observe the treatment response in patients with mRCC targeted treated with Sunitinib in first-line therapy.

Primary Objective:

- Evaluation of Sunitinib treatment responses/objective response rate according to disease risk group in patients with mRCC targeted treated with Sunitinib in first-line therapy in Turkey

Secondary Objectives:

- Evaluation of survival and treatment response to Sunitinib treatment regimen
- Determination of factors affecting the treatment regimen change and the frequency of these factors in patients with mRCC
- Determination of demographic, clinical and pathological characteristics of patients with mRCC
- Determination of median duration use of patients using IFN.

This is a non-interventional, retrospective, evaluational study, based on data extracted and analyzed from the RCC Registry.

This study was designed to answer the Sunitinib treatment responses/objective response rate according to disease risk group in patients with mRCC.

All patient data in the RCC Registry, meeting all of the inclusion criteria will be included in the study.

The variables to be obtained from this study:

- Demographic information (age, sex)
- Physical measurements (height and weight measurements)
- Disease and concomitant disease history (Hypertension, Diabetes mellitus)
- Previous treatments (Angiotensin Converting Enzyme Inhibitor (ACE-I) / Angiotensin Receptor Blockers (ARB), statin)
- Age of start of Sunitinib,
- Smoking history,
- Date of diagnosis
- Surgery type (Radical nephrectomy, partial nephrectomy)

PFIZER CONFIDENTIAL

- Histopathological information
 - Pathological type,
 - Pathological stage and location,
 - T size and location
 - Fuhrman Grade,
 - Adrenal involvement,
 - Lymph node (LN) involvement,
 - Number of LNs removed,
 - Sarcomatoid feature,
- Other involvement information
- Treatment given (order of treatment given, starting date, dose, dose changes, if available)
- Discontinuation of treatment information and the reason
- Previous IFN use
- Toxicities leading dose reduction and treatment discontinuation
- Information of risk (International Metastatic RCC Database Consortium (IMDC), Memorial Sloan Kettering Cancer Center (MSKCC) subgroups)
- Performance scores (Eastern Cooperative Oncology Group (ECOG))
- Metastasis site information
- Laboratory values, if available
- Survival status

RCC Registry will be used as data source for this study and the patient data will be retrospectively recorded in the study database.

The annual disease burden in contributing centers to RCC Registry is approximately 100 patient/center, the treatment of an average of 250 patients per year is continued in the centers. Therefore, it is estimated that information of 400 eligible patients that were registered in RCC Registry from 2019 to 2022 will be included in the analysis.

The Statistical Package for Social Sciences (SPSS) 19.0 for Windows will be used for the analysis. A type-I error of less than 5% will be interpreted as statistically significant. Normality of data will be tested using the visual (histogram and probability plots) and analytical (Kolmogorov-Smirnov/Shapiro-Wilk tests) methods. Descriptive statistics will be expressed as numbers and percentages for categorical variables and as mean and standard deviation for normally distributed numerical variables, median and interquartile range (IQR) for non-normally distributed numerical variables. For Survival Analyses, Kaplan-Meier estimates will be calculated and for survival rate comparison of Kaplan-Meier estimates within selected categorical groups will be investigated using log rank test.

5. AMENDMENTS AND UPDATES

Amendment number	Date	Protocol section(s) changed	Summary of amendment(s)	Reason
1	01 September 2021	3 8 6, 9.2	
- Responsible parties of protocol revised.- Research question and objectives revised.- Editing data collection and milestone dates	
- Principal investigators of the protocol added.- Objective of “Determination % of patients with PD-L1 positivity of 1% or more in mRCC patients.” added.- Changing the study starts, data collection and final study dates
2	18 November 2022	Study information, 2, 3, 4, 5, 6, 8, 9, 10, 11,	
- Study information revised.- List of abbreviations revised.- Responsible parties revised.- Editing abstract.	
- Study title edited.- Research question and objectives revised.- Author section revised and co-author information added.- Abbreviations edited.- Registry database information added.- Study objectives, variables, sample size revised.

		
- Editing data collection and milestone dates.- Research question and objectives revised.- Research methods revised.- Quality control revised.- Protection of human subjects information revised.	
- Study timeline revised.- Objectives revised- Editing study design and study setting details as a secondary data collection. Study redesigned as a registry based study instead of collecting data by archive screening in different centers, data sources revised.- Study schedule revised according to revised milestones.- Inclusion criteria section revised for the revised study design.- Variables that will be extracted from RCC Registry revised.- Study size, data management and quality control section revised- Editing patient information/consent, ethics subject.- Editing safety language of study due to revised study type .
--	--	---	---

			
- Management and reporting of adverse events/adverse reactions revised.
 
- Principal investigators of the protocol were revised.
	
-The collection of data in the study design based on a structured registry rather than patient records.

--	--	--	---	--

6. MILESTONES

Milestone	Planned date
Start of data collection	9 January 2023
End of data collection	13 February 2023
Final study report	01 April 2023

7. RATIONALE AND BACKGROUND

Due to the widespread use of cross-sectional radiology in recent years and the increase in the frequency of renal cell carcinoma (RCC) risk factors such as smoking and obesity, RCC is increasingly common. More than 200,000 people are diagnosed with RCC each year worldwide, and nearly half die because of this reason. RCC is the 7th most common cancer in men in Turkey (1).

RCC is one of the cancers in which classical cytotoxic chemotherapies are not effective. For this reason, it is among the tumors in which the treatments targeting the immune system are mostly studied together with melanoma. However, although it has been more viable in recent years, immunotherapy in RCC is not new. The first strong data that immunotherapy is effective in RCC is based on studies of high-dose interleukin 2 (HD IL-2) and interferon. In addition, rare cases of spontaneous regression suggest that immune targeted therapies can be an effective approach in RCC. Despite the low response rates, sustainability of long-term remission with HD IL-2 in 5-10% of patients, even after discontinuation of treatment, has led to the "first line" treatment in selected patients for many years, it became the first "class" approved for use in the treatment of metastatic RCC by the Food and Drug Administration (FDA) in 1992 (2). However, due to serious toxicities such as hypotension, renal dysfunction, respiratory distress like Acute respiratory distress syndrome (ARDS), HD IL-2 could only be used in "fit" patients and in certain centers and could not be widespread.

Motzer stated in his 1996 review that "immunomodulation" may have a role in the treatment of RCC (3). However, with the understanding of the role of vascular endothelial growth factor (VEGF) in the pathogenesis of the disease, following the "cytokine" based treatments in the nineties, the 2000s have been the years when treatments targeting the VEGF "class 2" and mTOR "class 3" pathways came to the fore. Thus, since 2005, 9 agents targeting these pathways have been approved by the FDA for the treatment of metastatic RCC.

Everolimus, the mTOR inhibitor, was the first agent approved for use in patients who progressed after tyrosine kinase inhibitors (TKIs) (4). Its use was approved by the FDA in 2009 with the advantage of a progression-free survival (PFS) of 4.9 months versus 1.9 months in the placebo controlled RECORD-1 study (5). Therefore, everolimus has become

the standard arm in many randomized studies conducted in the following years. Other VEGF-based agents with shown efficacy in the second step are, in the order of being approved by the FDA; axitinib, lenvatinib and cabozantinib (6). However, despite the high response rates achieved with targeted agents, the median PFS achieved with first-line VEGF-targeted therapies varies between 8-12 months and 5-7 months in the second-level, and progression is often inevitable (7). In recent years, it has been shown that the ability of cancer cells to escape from the immune system is one of the hallmarks of cancer, and studies showing that immune therapies are effective in many tumors have begun to come one after another. As we mentioned at the beginning, RCC is one of the first tumors in which immune therapies were used.

8. RESEARCH QUESTION AND OBJECTIVES

The purpose of this study is to observe the treatment response in patients with mRCC treated with Sunitinib in first-line therapy.

Primary Objective:

- Evaluation of Sunitinib treatment responses/objective response rate according to disease risk group in patients with mRCC treated with Sunitinib in first-line therapy in Turkey

Secondary Objectives:

- Evaluation of survival and treatment response to Sunitinib treatment regimen
- Determination of factors affecting the treatment regimen change and the frequency of these factors in patients with mRCC
- Determination of demographic, clinical and pathological characteristics of patients with mRCC
- Determination of median duration use of patients using IFN.

[figure not shown]

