9.2. Setting

Analysis for this study will be conducted on data anonymized and extracted from RCC Registry; time frame for this study data set is information of eligible patients that were registered in RCC Registry between March 2019 and October 2022.

RCC Registry is a data log where clinical information is recorded by inviting patients who meet the patient selection criteria according to registry protocol from 6 different centers since March 2019. In this study, RCC Registry will be used as sole data source.

The annual disease burden in contributing centers to RCC Registry is approximately 100 patient/center, the treatment of an average of 250 patients per year is continued in the centers. Therefore, it is estimated that information of approximately 400 eligible patients who were registered in RCC Registry from 2019 to 2022 will be included in the analysis.

Study Schedule GES / Timeline	November 2022	December 2022	January 2023	February 2023	March 2023	April 2023
Preparation phase and obtaining necessary approvals	X	X				
Extracting data from RCC Registry			X	X		
Data management, statistical analysis and reporting				X	X	X

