9.3. Variables

The following variables will be extracted from RCC Registry in the scope of this study:

- Demographic information (age, sex)
- Physical measurements (height and weight measurements)
- Disease and concomitant disease history (Hypertension, Diabetes mellitus)
- Previous treatments (ACE-I / ARB, statin)
- Age of start of Sunitinib,
- Smoking history,
- Date of diagnosis
- Surgery type (Radical nephrectomy, partial nephrectomy)
- Histopathological information
 - Pathological type,
 - Pathological stage and location,
 - T size and location
 - Fuhrman Grade,
 - Adrenal involvement,
 - Lymph node (LN) involvement,
 - Number of LNs removed,
 - Sarcomatoid feature,

- Other involvement information
- Treatment given (order of treatment given, starting date, dose, dose changes, if available)
- Discontinuation of treatment information and the reason
- Previous IFN use
- Toxicities leading dose reduction and treatment discontinuation
- Information of risk (International Metastatic RCC Database Consortium (IMDC), Memorial Sloan Kettering Cancer Center (MSKCC) subgroups)
- Performance scores (ECOG)
- Metastasis site information
- Laboratory values, if available
- Survival status

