9.7. Data analysis

The Statistical Package for Social Sciences (SPSS) 19.0 for Windows will be used for the analysis. A type-I error of less than 5% will be interpreted as statistically significant.

Normality of data will be tested using the visual (histogram and probability plots) and analytical (Kolmogorov-Smirnov/Shapiro-Wilk tests) methods. Descriptive statistics will be expressed as numbers and percentages for categorical variables and as mean and standard deviation for normally distributed numerical variables, median and interquartile range (IQR) for non-normally distributed numerical variables. For Survival Analyses, Kaplan-Meier estimates will be calculated and for survival rate comparison of Kaplan-Meier estimates within selected categorical groups will be investigated using log rank test.

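### No analysis is assigned to the regimen-change objective; the default n (%) links no factor to change and ignores unequal observation time

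*Combined protocol and SAP*

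**What the plan says.** The objective in section 8, repeated in the abstract, is "Determination of factors affecting the treatment regimen change and the frequency of these factors in patients with mRCC". Regimen change is not defined: it could be a dose change, stopping sunitinib, or starting the next line.

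Section 9.7 is the only analysis text, and Annex 1 lists no stand-alone documents. For categorical data it says "Descriptive statistics will be expressed as numbers and percentages for categorical variables". It adds mean and SD or median and IQR for numerical variables, and Kaplan-Meier estimates with log-rank tests for survival in categorical groups that it does not name. It contains no regression, no test of association for regimen change, no time-to-change analysis and no competing-risk method.

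The fields in section 9.3 include order of treatment, starting date, dose changes if available, "Discontinuation of treatment information and the reason", toxicities leading to dose reduction or discontinuation, risk group, ECOG, surgery type, previous IFN and survival status. Stop, death, last-contact and registration dates are not listed.

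Section 9.2 limits the data set to "eligible patients that were registered in RCC Registry between March 2019 and October 2022". Section 6 puts data collection between "9 January 2023" and "13 February 2023". No data cut-off, minimum follow-up or follow-up range is given. Section 9.2.2 removes patients who started treatment but were excluded from follow-up for any reason.

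**The concern.** The objective can be read in two ways, and section 9.7 serves neither well.

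If factors affecting change means determinants, an analysis must relate patient or disease characteristics to the occurrence of change. None is planned.

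If it means recorded reasons and how often they occur, numbers and percentages are the natural table. But a crude percentage of all patients treats someone still on sunitinib after three months the same as someone unchanged after nearly four years, and it counts death before a change as no change. The result then depends partly on how long patients happened to be observed. It would be hard to interpret by itself, to compare between risk groups whose observation times differ, or to set against another registry.

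**Working it through.** There is no figure in the plan to reproduce for this objective: no event rate, follow-up or precision is stated. The check has two parts.

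**1. Potential time since registration** (dates from sections 6 and 9.2; 30.44 days per month)

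| Assumed cut-off | Registered 31 Oct 2022 | Registered 1 Mar 2019 |
|---|---|---|
| 9 January 2023 | 2.3 months | 46.3 months |
| 13 February 2023 | 3.4 months | 47.5 months |
| 31 October 2022 | 0 months | 44.0 months |

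With a cut-off at extraction the range is about 2 to 47 months. This is inferred from the dates. It is time since registration, not time on sunitinib.

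**2. Illustration of what unequal observation does to a crude percentage**

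Assumptions: exponential time to change with median m; registration uniform over the window; cut-off 13 February 2023; no death before change. For m, section 7 says "the median PFS achieved with first-line VEGF-targeted therapies varies between 8-12 months". Using PFS as a proxy for time to change is an assumption of this review.

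Proportion unchanged at time t is 0.5^(t/m). Averaged over observation times from a to b:

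U = [0.5^(a/m) − 0.5^(b/m)] / [(ln 2/m)(b − a)], and the crude proportion changed is 1 − U.

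*Sunitinib starts at registration, m = 10 (ln 2/m = 0.0693):*

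- March–December 2019 registrants, a = 37.45, b = 47.47: U = (0.0746 − 0.0372)/(0.0693 × 10.02) = 0.054, so 95% changed.
- January–October 2022 registrants, a = 3.45, b = 13.40: U = (0.7874 − 0.3950)/(0.0693 × 9.95) = 0.569, so 43% changed.
- All registrants, a = 3.45, b = 47.47: U = (0.7874 − 0.0372)/(0.0693 × 44.02) = 0.246, so about 25% still unchanged. For m = 8 and m = 12 the same formula gives 19% and 30%.

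*Sunitinib started 12 months before registration, with registration unrelated to change status, m = 10:* each U is multiplied by 0.5^(12/10) = 0.435.

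- 2019 registrants: 0.054 × 0.435 = 0.023, so about 98% changed.
- 2022 registrants: 0.569 × 0.435 = 0.248, so about 75% changed.

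The gap between the two groups, with the same underlying rate of change, falls from about 52 points to about 23.

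**The case against.** Section 9.7 does not say that this objective will be reported as crude counts; it says nothing about it. That is right. The supportable complaint is that no method is specified, and that numbers and percentages are what remains by default. The Kaplan-Meier and log-rank sentence could be stretched to time to discontinuation, but it is worded for survival and names no groups.

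A reader might infer that follow-up runs from 3 to 47 months and that the frequencies simply reflect registration date. The documents do not support this. No cut-off is given, and section 9.2.1 does not require sunitinib to start at or after registration. Section 9.2 also describes centers continuing the treatment of existing patients. Registration date may therefore be only loosely tied to time on drug, and the 12-month-lag case shows the effect shrinking.

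The illustration concerns the percentage who changed, whereas the objective asks for the frequency of factors. A table of reasons among those who changed, with follow-up reported, is a legitimate descriptive answer under the narrower reading. This stands, and it is why the fix offers rewording as an alternative. A reader might go on to claim that early reasons such as toxicity would be over-represented. The documents give nothing on when changes for each reason occur, so that claim is not made here.

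A multivariable model is also only one option for a secondary objective in a retrospective study. But if determinants are meant, some analysis of association is needed, and none is planned.

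**Conclusion.** The point holds in a limited form. Section 9.7 assigns no analysis to the regimen-change objective, and the one method that fits by default neither links any factor to change nor handles unequal observation time. This rests on the text alone.

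How far crude frequencies would be distorted is not known. They would depend partly on length of observation. The figures of 95% against 43%, and about 98% against 75% with a 12-month lag, show that the effect can be material. They rest on an assumed exponential model, a 10-month median borrowed from PFS, uniform registration, a cut-off on the last extraction day and no death before change. They are not predictions for this registry.

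The objective is secondary, so this should be corrected before extraction but does not undermine the primary objective.

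**What to change.** In section 9.7:

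1. Define regimen change for analysis (for example, discontinuation of sunitinib or start of the next line), the time origin (sunitinib start) and the data cut-off.
2. Report cumulative incidence of change by recorded reason at 6, 12 and 24 months, with death before change as a competing event. Where sunitinib began before registration and the patient was enrolled while still on it, use left truncation at registration.
3. Fit a cause-specific Cox model for change on a short pre-listed set of baseline variables from section 9.3, such as IMDC group, age, ECOG, nephrectomy and previous IFN.
4. Keep n (%) of reasons among those who changed as a supporting table.

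In sections 9.3 and 9.6, add stop, death and last-contact dates to the extraction list, and the registration date needed for left truncation. In section 9.2.2, censor patients lost to follow-up at last contact instead of excluding them.

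If the objective is meant only as recorded reasons, reword it in section 8 and omit the Cox model.

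The cost is more analysis work and dependence on those dates being held in the registry. No extra patients are needed. Treatment starting dates and most of the baseline variables are already listed, and the planned survival analysis needs death and last-contact dates in any case.
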